12.8 Committees related to safety

12.8.1 Novo Nordisk safety committee

Novo Nordisk has constituted an internal concizumab safety committee to perform ongoing safety surveillance of safety data relevant to concizumab. The safety committee is a cross functional group within Novo Nordisk.

12.8.2 Data monitoring committee

The DMC is an independent, external committee composed of members whose expertise covers relevant specialties including statistics. The DMC is established to review and evaluate accumulated data from the trial at predefined time points as well as ad-hoc. This is in order to protect the safety of the patients and to evaluate the benefit-risk balance. The DMC will have access to the unblinded data, and will provide recommendations on trial continuation, modification or termination.

In case there is any safety concern data will be compiled and the DMC will review these data. Their recommendation will go to the Novo Nordisk Safety committee for final decision of what next step is in this trial.

The DMC members will only have direct contact with the Novo Nordisk Global Safety department through the safety surveillance representatives, and will have no direct interaction with those in trial management. The DMC recommendations should be addressed directly to the Novo Nordisk Global Safety department and the internal Novo Nordisk safety committee for concizumab. It is the responsibility of the Novo Nordisk internal safety committee for concizumab to take action(s) for patient safety based on the DMC recommendations.

Information regarding responsibilities, procedures and workflow to be used by the DMC are specified in the DMC charter.

Protocol
 Trial ID:NN7415-4255
 UTN:U1111-1179-3872
 EudraCT no.:2016-000614-29

~~CONFIDENTIAL~~

Date:	05 May 2017	Novo Nordisk
Version:	2	
Status:	Final	
Page:	94 of 124	

13 Case report forms

For this trial a combination of electronic case report forms (eCRFs) and paper CRFs will be used.

Novo Nordisk will provide a system for the electronic case report forms (eCRF). This system and support services to the system will be provided by an external supplier.

Ensure that all relevant questions are answered, and that no empty data field exists. If a test or an assessment has not been done and will not be available, or if the question is irrelevant (e.g. is not applicable), indicate this according to the data entry instructions.

The following will be provided as paper CRFs to be used when access to the eCRF is revoked or if the eCRF is unavailable:

- AE forms
- Safety information forms
- Technical complaint forms

On the paper CRF forms print legibly, using a ballpoint pen. Ensure that all questions are answered, and that no empty data blocks exist. Ensure that no information is recorded outside the data blocks. If a test/assessment has not been done and will not be available, indicate this by writing “ND” (not done) in the appropriate answer field in the CRF. If the question is irrelevant (e.g. is not applicable) indicate this by writing “NA” (not applicable) in the appropriate answer field. Further guidance can be obtained from the instructions in the CRF.

The investigator must ensure that all information is consistent with the source documentation. By electronically signing the case book in the eCRF, the investigator confirms that the information in the eCRF and related forms is complete and correct.

13.1 Corrections to case report forms

Corrections to the eCRF data may be made by the investigator or the investigator’s delegated staff. An audit trail will be maintained in the eCRF application containing as a minimum: the old and the new data, identification of the person entering the data, date and time of the entry and reason for the correction.

If corrections are made by the investigator’s delegated staff after the date the investigator has signed the case book, the case book must be signed and dated again by the investigator.

13.2 Case report form flow

The investigator must ensure that data is recorded in the eCRF as soon as possible, preferably within 5 days after the visit. Once data has been entered, it will be available to Novo Nordisk for data verification and validation purposes.

Protocol
 Trial ID:NN7415-4255
 UTN:U1111-1179-3872
 EudraCT no.:2016-000614-29

~~CONFIDENTIAL~~

Date:	05 May 2017	Novo Nordisk
Version:	2	
Status:	Final	
Page:	95 of 124	

Site specific eCRF data (in an electronic readable format) will be provided to the trial site before access to the eCRF is revoked. This data must be retained at the trial site.

13.3 Electronic diary

Novo Nordisk will provide the patient with an eDiary for electronic recording of details of their home treatment, bleeding episodes and treatment of bleeding episodes (i.e. use of FVIII). The eDiary and related support services will be supplied by a vendor working under the direction and supervision of Novo Nordisk.

Patients will be instructed in the use of the eDiary by the investigator or delegated person before entering of any data. The eDiary will be dispensed to the patient at visit 2. After visit 2 and onwards, data will be entered by the patient in the eDiary device during home treatment.

The eDiary will be returned by the patient at the end of trial (EOT) visit.

All data entered will be transferred from the device to an electronic database, where it is kept as a certified copy of the source data by the eDiary vendor. Data entered in the device will upon confirmation of a successful back-up be deleted from the device.

The eDiary will have built in edit checks and reminders, to ensure that all relevant questions are answered.

eDiary data transferred to the electronic database will be viewable to relevant trial site staff and Novo Nordisk personnel on a secure, password protected web portal.

13.3.1 Investigator review of eDiary data

It is the responsibility of the Investigator or delegated staff to review the eDiary data reported by the patient. As a minimum it must be verified that the eDiary data is complete, consistent and according to the requirements defined in this protocol. This also includes that the number of doses reported in the eDiary is reviewed against the number of vials/cartridge accounted for as used by the patient. Upon review the Investigator must document that the review has taken place and any actions required e.g. retraining of the patient or decision to amend or correct the data reported by the patient.

If the Investigator finds it necessary to amend or correct eDiary data, the patient must be consulted prior to requesting the actual data change. A Data Correction Request must be submitted to the eDiary vendor. An audit trail will be maintained.

14 Monitoring procedures

Monitoring will be conducted using a risk based approach including risk assessment, monitoring plans, centralised monitoring and visits to trial sites. During the course of the trial, the monitor will

Protocol
Trial ID:NN7415-4255
UTN:U1111-1179-3872
EudraCT no.:2016-000614-29

~~CONFIDENTIAL~~

Date:	05 May 2017	Novo Nordisk
Version:	2	
Status:	Final	
Page:	96 of 124	

visit the trial site to ensure that the protocol is adhered to, that all issues have been recorded, to perform source data verification and to monitor drug accountability. The first monitoring visit will be performed as soon as possible after FPFV at the trial site and no later than 4 weeks after. The monitoring visit intervals will depend on the outcome of the centralised monitoring of the eCRFs (remote assessment of data by Novo Nordisk), the trial site's recruitment rate and the compliance of the trial site to the protocol and GCP, but will not exceed 12 weeks until LPLV at the trial site. This only applies to sites with scheduled, ongoing and/or discontinued patients.

The monitor must be given direct access to all source documents (original documents, data and records). Direct access includes permission to examine, analyse, verify and reproduce any record(s) and report(s) that are important to the evaluation of the trial. If the electronic medical record does not have a visible audit trail, the investigator must provide the monitor with signed and dated printouts. In addition the relevant trial site staff should be available for discussions at monitoring visits and between monitoring visits (e.g. by telephone or text message).

All data must be verifiable in source documentation other than the eCRF. eDiary data is entered by the patient and will also be treated as source data.

For all data recorded the source document must be defined in a source document agreement at each trial site. There must only be one source defined at any time for any data element.

For historical data such as medical history, details of haemophilia and haemophilia treatment history, a reasonable effort must be made by the investigator, considering local requirements, to obtain this information from external sources, if not known by the patient. It is accepted that the earliest practically retainable record should be considered as the location of the source data and therefore the source document. This means that for laboratory results (e.g. biochemistry and haematology) a signed printout of the electronic results must be available.

Source data generated by the trial site can be corrected by another person than the person entering the source data if accepted by local regulations; any correction must be explained, signed and dated by the person making the correction.

The monitor will ensure that the eCRFs are completed and paper CRFs (if any) collected, that PROs and eDiaries are completed and reviewed by the investigator at the relevant scheduled visits and needed action has been taken and documented, if any.

The following data will be source data verified for screening failures:

- Date for obtaining informed consent
- Inclusion and exclusion criteria
- Screen failure reason if possible
- Date patient left the trial
- Data relating to AEs if applicable

Protocol
Trial ID:NN7415-4255
UTN:U1111-1179-3872
EudraCT no.:2016-000614-29

~~CONFIDENTIAL~~

Date:	05 May 2017	Novo Nordisk
Version:	2	
Status:	Final	
Page:	97 of 124	

- Demography (See section [8.2.1](#))
- Date of visit

Monitors will review the patient's medical records and other source data (e.g. eDiaries and ePROs) to ensure consistency and/or identify omissions compared to the eCRF. If discrepancies are found, the investigator must be questioned about these.

A follow-up letter (paper or electronic) will be sent to the investigator following each monitoring visit. This should address any action to be taken.

Protocol
 Trial ID:NN7415-4255
 UTN:U1111-1179-3872
 EudraCT no.:2016-000614-29

~~CONFIDENTIAL~~

Date:	05 May 2017	Novo Nordisk
Version:	2	
Status:	Final	
Page:	98 of 124	

15 Data management

Data management is the responsibility of Novo Nordisk. Data management may be delegated under an agreement of transfer of responsibilities to a contract research organisation (CRO).

Appropriate measures, including encryption of data files containing person identifiable data, will be used to ensure confidentiality of patient data, when they are transmitted over open networks.

Data from central laboratories will be transferred electronically. In cases where data is transferred via non-secure electronic networks, data will be encrypted during transfer.

The laboratory will provide all laboratory reports to the investigator for filing at the trial site. The laboratory report must be signed and dated by the investigator or delegated person and stored at the trial site as source data.

The patient and any biological material obtained from the patient will be identified by patient number and trial ID. Appropriate measures such as encryption or leaving out certain identifiers will be enforced to protect the identity of patients in all presentations and publications as required by local, regional and national requirements

16 Computerised systems

Novo Nordisk will capture and process clinical data using computerised systems that are described in Novo Nordisk Standard Operating Procedures and IT architecture documentation. The use and control of these systems are documented.

Investigators working on the trial may use their own electronic systems to capture source data.

Novo Nordisk will use the Global Haemophilia Network (GHN) Investigator Portal to distribute and share trial-related documents and information with the participating sites.

After trial completion, Novo Nordisk will supply each trial site with long-life CDs or other relevant electronic archiving containing the electronic Investigator Trial Master File (eITMF) for each trial site. These CDs or other relevant electronic archiving will contain site-specific trial documentation as well as trial specific news and other relevant trial information, including audit trail on documents and site staff users. The GHN Portal software and hardware implementation are compliant with the requirements of U.S. Food and Drug Administration (FDA) 21 CFR Part 11 and ICH E6 (EU directive for personal data protection)^{1, 29}.

Novo Nordisk will provide electronic tablets for reporting of all PROs questionnaires described in section [8.6.1](#) and in [Appendix 1](#). In case the electronic tablet is revoked the questionnaires will be available in paper.

Protocol
 Trial ID:NN7415-4255
 UTN:U1111-1179-3872
 EudraCT no.:2016-000614-29

~~CONFIDENTIAL~~

Date:	05 May 2017	Novo Nordisk
Version:	2	
Status:	Final	
Page:	99 of 124	

The eDiary software and hardware implementation are compliant with the requirements of FDA 21 CFR Part 11 and ICH E6 (EU directive for personal data protection)^{1, 29}. After trial completion, each trial site will be supplied with long-life CDs. These CDs will contain site-specific patient records including the patient's eDiaries and ePROs as PROs are handled separately from eDiary and audit trail including any data additions and corrections made on each form. The eDiary vendor will furthermore retain and securely store copies of all archived documents and data for 15 years or as required by local data retention laws for trial data

17 Statistical considerations

All endpoints referring to a time frame of at least 24 weeks will be evaluated in the main part of the trial, defined to end when the last patient have completed a minimum of 24 weeks of dosing or at LPFT (visit 2)+24 weeks if the last patient has withdrawn before visit 9. Please refer to [Figure 17-1](#) for further information. All available data up to the time point where the last patient ends 24 weeks of treatment or has withdrawn will in such case be used in the analysis of the main part.

Endpoints comprising number of bleeding episodes will be evaluated based on treated bleeding episodes only. Multiple bleeding locations occurring from the same event (e.g., due to a bicycle accident) or at the same time point will be counted as one bleeding episode. Further, the endpoints will not include re-bleed.

A re-bleed is defined as a bleeding episode (worsening of bleeding site conditions e.g. swelling, pain) within 72 hours after stopping of a previous bleeding episode at the same (or subset of the same) anatomical location. If a bleeding episode occurs in the same location 72 hours after stopping, the treatment is defined as a new bleeding episode.

Clinical proof of concept

The statistical analysis of the collected data aims to establish CPoC that concizumab is efficacious in preventing bleeding episodes in haemophilia A patients without inhibitors. The objective will be assessed when the last of the 30 patients have completed 24 weeks of dosing (or have withdrawn).

Two criteria will be evaluated in a hierarchical fashion in support of CPoC comprising a comparison of the ABR of all patients with a threshold of 12, irrespective of individual dose titration. The primary CPoC criterion aims at evaluating the effect of concizumab at the last dose level reached for a patient. Hence, for this evaluation, only observations from the period where patients are on their end dose at time of analysis will contribute to the analysis. Furthermore, observations from the 2 week run-in period will be not be included. Since this evaluation disregards a subset of data collected the result should be viewed taking in to account the potential bias. The second CPoC criterion aims at evaluating the effect of concizumab when given as an escalation regimen. Hence, this will compare the ABR of haemophilia A patients treated with concizumab with the typical historical ABR of haemophilia A patients being treated on-demand using all data after enrolment. The second CPoC criterion will only be evaluated if the first one succeeds.

Protocol
 Trial ID:NN7415-4255
 UTN:U1111-1179-3872
 EudraCT no.:2016-000614-29

~~CONFIDENTIAL~~

Date: 05 May 2017
 Version: 2
 Status: Final
 Page: 100 of 124
 Novo Nordisk

The referred comparisons will be made using a negative binomial model with log of *exposure time in main phase* as offset. For each criterion, evidence of effect will be concluded if the 95% confidence interval of the estimated ABR is below 12.

The value of 12 bleeds per year reflects conservatively a 50% reduction from the bleeding rate during on-demand treatment, which in previous trials typically has been reported to be above 30 bleeds per year³⁰⁻³². A confidence limit lower than 12 will also to a certain extent substantiate that the prophylactic efficacy of concizumab may be similar to that of FVIII replacement therapy where an estimated mean of 6.5 bleeds per year was observed³³.

Clinical arguments for the hierarchical test approach

Concizumab exhibits non-linear PK due to target mediated drug disposition and it is expected that the dose response curve of the ABR is rather steep. This implies that patients that are on a dose which is not efficacious are likely to bleed as patients that are not treated at all. The subset of data collected from the last dose clinically deemed as efficacious would reflect the efficacy of concizumab in the given patient.

17.1 Sample size calculation

The sample size calculation has been determined taking the small patient population into account, while also aiming for an acceptably narrow 95% confidence interval for the ABR.

Sufficient inference on bleeding episodes for the primary CPoC criterion is judged to be accommodated by 30 patients.

It is expected that the treatment duration of the main part allowing for escalation time for some patients is on average 6 months in the below calculations.

When evaluating the power of the negative binomial analysis referred above, an annual bleeding rate of 4 is assumed for the end dose concizumab regimen, respectively in combination with an over-dispersion of 6. The power for concluding a bleeding rate lower than 12 then becomes approximately 95%. The power under varying values of true ABR and over-dispersion for the primary CPoC criterion are shown below in [Table 17-1](#).

Table 17-1 Power in comparison between concizumab prophylaxis treatment and an ABR threshold of 12 under different assumptions of ABR and over-dispersion.

Power	Over-dispersion		
	5	6	7
4	99%	95%	92%
5	95%	90%	86%
6	87%	81%	72%

Protocol
 Trial ID:NN7415-4255
 UTN:U1111-1179-3872
 EudraCT no.:2016-000614-29

~~CONFIDENTIAL~~

Date:	05 May 2017	Novo Nordisk
Version:	2	
Status:	Final	
Page:	101 of 124	

For the secondary CPoC criterion that includes data prior to potential dose escalation, it is expected that the treatment duration of the main part is on average 8 months with an average ABR of 5.4 for the concizumab treated patients. This yields a marginal power of approximately 87% for the secondary CPoC criterion.

In prior Novo Nordisk trials conducted in haemophilia patients, the typical 1-year over-dispersion for non-inhibitor patients on prophylaxis with FVIII or FIX has been in the range 4-8, implying 24 weeks over-dispersion of 3-5 (e.g. in NN7008-3543, NN7088-3859 and NN7999-3747). On that background, an over-dispersion of 6 over the 24 weeks in the main part of the current trial is deemed realistic.

17.2 Definition of analysis sets

All dosed patients will be included in the Full Analysis Set (FAS) as well as in the Safety Analysis Set (SAS).

17.3 Primary endpoint

The primary endpoint is the number of bleeding episodes during at least 24 weeks from treatment onset.

The primary endpoint will be estimated using negative binomial regression with log of *exposure time in main phase* as offset, providing an actual estimate of the ABR as well as a corresponding 95% confidence interval.

This analysis has the underlying assumption that the missing data mechanism is “missing at random”, i.e. MAR. Under this assumption, the statistical behaviour of the missing data (given the observed responses and the mean value structure) is assumed to be the same as for the observed data. The endpoint will be estimated based on the full analysis set (FAS) and only data collected prior to discontinuation of trial product or initiation of alternative treatment options will be used to draw inference.

17.4 Sensitivity analyses

To evaluate the robustness of the MAR assumption implied in the primary analysis, a modified tipping point analysis will be performed where patients having discontinued before finalization of the main part are assumed to have a worse outcome compared to what was observed during the main part of the trial. This will be done by adding a value Δ_i to the observed bleeding episodes in the main part of the trial before analysing the data. The offset is maintained as being the exposure during the main phase since it is not possible to identify the amount of missing observation time. The degree of worsening, Δ_i , will gradually be increased to evaluate at which point the upper 95% confidence limit of the prophylactic concizumab ABR is no longer below a threshold of 12.

Protocol
 Trial ID:NN7415-4255
 UTN:U1111-1179-3872
 EudraCT no.:2016-000614-29

~~CONFIDENTIAL~~

Date: 05 May 2017
 Version: 2
 Status: Final
 Page: 102 of 124

Novo Nordisk

The results of the primary analysis will be considered robust if the tipping point is above what is considered clinical plausible.

17.5 Additional analyses

An additional evaluation of the primary endpoint will be made, including actual concizumab dose level as *additional factor in the primary analysis model specified above*. Point estimates and 95% confidence interval will be provided for the ABR at the different dose levels of concizumab (0.15, 0.20 and 0.25 mg/kg). Furthermore, an analysis with individual steady state PK/PD assessments included as covariates in the negative *binomial regression model as specified for the primary analysis* will be performed in order to evaluate possible associations between PK/PD and ABR that potentially could guide dose-selection. The referred steady-state PK/PD assessments comprise the concizumab trough level, maximum plasma concentration (C_{max}) of concizumab, TFPI value prior to the last s.c. dose administration, peak thrombin generation (nM), Endogenous thrombin potential (nM*min) and velocity index (nM/min).

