Due to the high between-patient variability in concizumab concentration observed in explorer^{TM3}, a significant overlap in plasma concentrations of concizumab in patients who received 0.25, 0.5 and 0.8 mg/kg doses was seen, see [Figure 5-2](#). Therefore, choosing three doses that would lead to reasonably distinct mean plasma concentrations of concizumab, and thus different efficacy at each dose level was not deemed possible. For this reason, a traditional parallel arm design was not chosen for the phase 2 trials. In contrast, the titration trial design allows patients to start on a low dose, which is expected to ensure prophylaxis but not marked changes in coagulation parameters, for the majority of patients. Escalation to the next dose level will only occur in the case of lack of efficacy (≥ 3 spontaneous bleeding episodes within the preceding 12 weeks). In addition, the PK of concizumab is heavily influenced by target mediated drug disposition, which means that small differences in concizumab dose ultimately leads to large differences in plasma concentrations. Therefore, daily dosing is proposed for the phase 2 trial, explorer^{TM5}. Daily dosing will allow for the increase in trough levels and thus better efficacy may be expected with a lower dose.

Embryonic exposure in pregnant female partners of men treated with concizumab is highly unlikely and there is no need for protocol requirements for use of contraception in phase 2 and 3 trials.

Protocol
 Trial ID: NN7415-4255
 UTN: U1111-1179-3872
 EudraCT no.: 2016-000614-29

~~CONFIDENTIAL~~

Date: 05 May 2017 | **Novo Nordisk**
 Version: 2
 Status: Final
 Page: 33 of 124

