5.3.1 Dose escalation

Bleeding episodes will be assessed during the trial both at scheduled visits and also between visits. The first 2 weeks of the treatment with concizumab 0.15 mg/kg is considered as a run-in period. Hence the bleeding episodes occurring during the first 2 weeks should not influence a dose escalation decision.

All spontaneous bleeding episodes (sBEs) are counted from 2 weeks after visit 2 (first-dose visit) until visit 16 (end-of-treatment visit), i.e. a total of 74 weeks. Dose-escalation will be based on the number of spontaneous, treated bleeding episodes in patients within preceding 12 weeks. However, before dose-escalation can occur, to ensure the safety of the patients, the investigator must take into account the full clinical picture the patient is presenting with and all available laboratory results, including coagulation parameters.

Dose 0.15 mg/kg:

When a sBE occurs, the investigator will determine if ≥ 3 sBEs have occurred within the preceding 12 weeks since visit 2+2weeks (including the current sBE). If yes, and if investigator deems it safe, the patient will have to be dose escalated from 0.15 to 0.20 mg/kg at the next scheduled visit. If the investigator judges that this visit is scheduled too late, he/she should contact the patient for an unscheduled visit.

Dose 0.20 mg/kg:

When an sBE occurs, the investigator will determine if ≥ 3 sBEs have occurred within the preceding 12 weeks (including the current sBE), counting only new sBEs from the beginning of the 0.20 mg/kg treatment period. If yes, and if investigator deems it safe, the patient will have to be dose escalated from 0.20 to 0.25 mg/kg at the next scheduled visit. If the investigator judges that this visit is scheduled too late, he/she should contact the patient for an unscheduled visit.

Dose 0.25 mg/kg:

Patients are not dose escalated further regardless of the number of sBEs. When an sBE occurs, the investigator will determine if ≥ 3 sBEs have occurred within the preceding 12 weeks (including the current sBE), counting only the new sBEs from the beginning of the 0,25mg/kg treatment period. If yes, then the patient must be discontinued from treatment due to lack of efficacy, see Section [6.4](#).

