17.8 Interim analysis

The trial does not include a formal interim analysis. However, the split of the trial into a main and extension part offers the opportunity of reporting results before the end of the trial. Other reporting of the trial might be done during the extension part once the data collection and review of the main part data has been finalised and individual clinical study reports might in such case be issued. A final clinical study report describing results from the main and extension part will be written when the last patient has either completed or withdrawn from the trial.

All main conclusions regarding clinical proof of concept and dose guidance for phase 3 will be based on the reporting after the main part, see [Figure 17-1](#).

[figure not shown]

Figure 17-1 Definition of main and extension part

Protocol
Trial ID:NN7415-4255
UTN:U1111-1179-3872
EudraCT no.:2016-000614-29

~~CONFIDENTIAL~~

Date: 05 May 2017
Version: 2
Status: Final
Page: 107 of 124

Novo Nordisk

18 Ethics

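### Dose-level ABRs in section 17.5 are confounded by escalation: patients reach 0.20 and 0.25 mg/kg only because they bled, and the planned model does not allow for it

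*Protocol*

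**What the plan says.** References are to Protocol version 2.0 (05 May 2017); section 17.5 reads the same in version 1.0.

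- Section 17.5 specifies the dose analysis: "An additional evaluation of the primary endpoint will be made, including actual concizumab dose level as" an extra factor in the primary model. Section 17.3 defines that model as negative binomial regression with log exposure as offset. Neither section names a patient effect, a baseline bleed rate or any adjustment for earlier bleeding. The output is: "Point estimates and 95% confidence interval will be provided for the ABR at the different dose levels of concizumab (0.15, 0.20 and 0.25 mg/kg").
- The same section puts individual steady-state PK/PD values into that model "in order to evaluate possible associations between PK/PD and ABR that potentially could guide dose-selection".
- Section 5.3.1 sets how dose is assigned: "Dose-escalation will be based on the number of spontaneous, treated bleeding episodes in patients within preceding 12 weeks". At 0.15 mg/kg, "the investigator will determine if ≥ 3 sBEs have occurred within the preceding 12 weeks since visit 2+2weeks (including the current sBE"); after the first step only new bleeds count. Section 5.2 confirms it: "Escalation to the next dose level will only occur in the case of lack of efficacy".
- At 0.25 mg/kg the same count ends treatment (5.3.1): "If yes, then the patient must be discontinued from treatment due to lack of efficacy".
- Section 17.8 states: "All main conclusions regarding clinical proof of concept and dose guidance for phase 3 will be based on the reporting after the main part".

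**The concern.** All patients start at 0.15 mg/kg, and the outcome itself moves them upward. Men who bleed rarely stay at 0.15. Men who bleed often supply nearly all the data at 0.20 and 0.25. Without a patient-level term, the dose coefficient mixes what the dose does with who was given it, and section 17.1 assumes large between-patient variation. Section 5.2 explains why parallel dose arms were not chosen, so no randomised comparison within the trial can correct the picture. The one bias warning in section 17 concerns data left out of the primary proof-of-concept criterion, not these models.

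At stake is the by-dose reading that goes into the phase 3 decision. A table with confidence intervals could show bleeding rising with dose when the doses work equally well, or hide a real gain from a higher dose.

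**Working it through.** **1. Check of the plan's own figure.** Section 17.1 gives n = 30, 6 months, ABR 4 and over-dispersion φ = 6, with power of about 95% to show ABR below 12.

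- Mean count μ = 4 × 0.5 = 2.
- SE of log rate = √(φ/(nμ)) = √(6/60) = 0.316.
- Power = Φ[(ln(12/4) − 1.96 × 0.316)/0.316] = Φ(1.51) = 93.5%. Simulated negative binomial fits give 96.0%.

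The stated figure is reproduced, so φ means variance/mean. The implied gamma shape for patient rates is μ/(φ − 1) = 2/5 = 0.4, a very wide spread between patients.

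**2. Set-up with no dose effect.** Each simulated patient has one gamma-distributed bleed rate that is the same at all three doses. From the protocol I took:

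- the 2-week run-in, the escalation rule and the stop at 0.25 mg/kg (5.3.1);
- the visit schedule (8.1.9 and 8.1.10);
- main-part follow-up of 24 to about 41 weeks (24 weeks plus the 4-month recruitment in section 7).

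The share of bleeds that are spontaneous is not in the documents. I assumed 75% and varied it from 50% to 100%. Section 17.5 does not say whether the dose factor uses all dose periods or only the end dose, so both were fitted.

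**3. Large-sample result** (true ABR 4 at every dose, φ = 6, 75% spontaneous):

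| Model | 0.15 | 0.20 | 0.25 |
|---|---|---|---|
| Planned model, by dose period | 3.9 | 15.7 | 24.5 |
| Planned model, end dose only | 1.7 | 8.3 | 23.9 |
| Dose periods with shared patient effect | 4.1 | 4.1 | 4.1 |

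The mechanism shows directly: grouped by end dose, the patients' own true mean rates are about 2.0 / 10.0 / 20.9, although dose changes nothing.

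**4. Sensitivity.** ABR was varied over 4–6, φ over 3–6 and the spontaneous share over 50–100%. The false ratios were:

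| Ratio | By dose period | By end dose |
|---|---|---|
| 0.20 vs 0.15 | 1.9 to 4.6 | 2.2 to 5.3 |
| 0.25 vs 0.15 | 2.6 to 7.2 | 4.4 to 16 |

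Removing the stopping rule leaves the gradient (3.9 / 15.7 / 21.9 by dose period). With almost no between-patient variation (φ = 1.05) it vanishes (4.1 / 4.3 / 3.5).

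**5. Trials of 33 patients.** Four scenarios of 600 trials each were run: ABR 4 with φ = 6 at 50% and at 75% spontaneous, ABR 5.4 with φ = 6 at 75%, and ABR 4 with φ = 3 at 75%. Among trials with an estimate, 0.20 looked worse than 0.15 in at least 96%. The 95% interval lay wholly above a ratio of 1 in 24–56% (dose period) or 45–62% (end dose), against a nominal 2.5% in that direction.

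**6. Concentration covariate.** Section 5.2 (footnote to Figure 5–2) puts typical exposure at a quarter of that in the highest explorer 3 cohort for 0.15 mg/kg, and below 40% and 70% for the next doses. Taking those limits, the ratio is about 1 : 1.6 : 2.8. With no true effect, ABR 4, φ = 6 and 75% spontaneous, the fitted ABR ratio per doubling of concentration is 1.86, 1.30 and 1.18 at assumed within-dose CVs of 50%, 100% and 150%. The protocol calls variability high but does not quantify it. PD covariates were not tested.

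**7. A steep response.** Assume 70%, 15% and 10% of patients first respond at 0.15, 0.20 and 0.25, and 5% never do. Assume about 25 bleeds a year without response and 2 with it. The population ABRs are:

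- 0.15: 0.70 × 2 + 0.30 × 25 = 8.9
- 0.20: 0.85 × 2 + 0.15 × 25 = 5.45
- 0.25: 0.95 × 2 + 0.05 × 25 = 3.15

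The planned model gives about 8.6 / 14.4 / 11.6, which reverses the first step. The shared-effect model gives about 8.4 / 3.9 / 1.6: the right order, but flattering to the higher doses.

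**The case against.** - **These are additional analyses.** Section 17.5 has no role in the proof-of-concept decision. That stands and limits the weight of the point.
- **The purpose is softer than it looks.** The phrase about guiding dose selection belongs to the PK/PD model. The dose-level ABRs carry no stated purpose and reach phase 3 only through the general statement in section 17.8, which covers all main-part reporting. That stands too.
- **A SAP could add detail.** Record layout and within-patient correlation are normally settled there, and this protocol does not say that a patient's periods are treated as independent. I do not claim that it does. But the model form is fixed here as the primary model plus dose, and both possible layouts are distorted.
- **The remedy's recovery of 4.1 / 4.1 / 4.1 is built in,** because the data came from the same kind of model. That is fair. Step 7 shows that it is model-dependent under a threshold response, though still closer to the right ordering than the planned model.
- **Little data will exist at higher doses.** At ABR 4, about 5 of 33 patients reach 0.20 mg/kg and 2 reach 0.25. This limits any analysis and is a further reason not to present the unadjusted figures as a comparison of doses.

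**Conclusion.** The dose-level ABRs in section 17.5 are confounded by the bleeding that triggers escalation. With equal efficacy and the plan's own ABR and over-dispersion, the model produces a false 4-fold difference between 0.20 and 0.15 by dose period (15.7/3.9) and about 5-fold by end dose (8.3/1.7). This rests on between-patient variation, which the plan assumes, and on an assumed spontaneous share; no value tried from 50% to 100% removes it.

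Four stronger readings go too far:

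- A reader might infer that the highest dose must look worst. That holds when the doses are equally effective; in the steep-response example 0.25 did not look worst, although the pattern was still wrong.
- A reader might infer that the intervals will exclude the truth. They do so in about 24–62% of trials, far too often but not always.
- A reader might infer an equally strong bias for the PK/PD covariates. For concentration it is about 1.2- to 1.9-fold per doubling, depending on an unstated CV; for PD it is unknown.
- A reader might infer that the proof-of-concept test is compromised by this. It does not use these models.

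**What to change.** In section 17.5:

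- Analyse one record per patient and dose period, including periods before escalation, with log(time at that dose) as offset and a shared patient random effect. Report within-patient dose rate ratios with intervals. Keeping the earlier periods matters, because the bleeds that triggered escalation must be in the likelihood.
- Keep the unadjusted ABRs by dose level if wanted, labelled as descriptive and not for comparing doses.
- Put PK/PD covariates into the same model where period-specific values exist. Otherwise state that the association is confounded by escalation. Sections 8.5.2.8 and 8.1.9.4 specify pre-dose concizumab samples only at visits 2, 9 and 16, with home dosing continuing regardless of visits 4–8, so pre-escalation troughs are not assured.
- State that the shared-effect result depends on the model, and that under a threshold response it can flatter higher doses.

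The cost is a wording change and a standard mixed count model on bleeds, doses and dates that are already collected. The downside is wide intervals, and at ABR 4 some trials would have no patient at 0.25 mg/kg.
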